#### ***Additional Analyses:***

- Baseline and 12-week cardiopulmonary testing to assay  $VO_{2\max}$  and anaerobic thresholds.
- Baseline and 12-week serum quantitative metabolomic profiling, pre- and post-CPET to evaluate whether NR increases the rate of oxidative phosphorylation.
- Baseline and 12-week quantitative serum cytokine immunoassay profiling to assess whether NR blunts HF linked inflammation.
- Skin biopsy at baseline and research blood at baseline and 12 weeks explore the effects of NR on oxidative phosphorylation and inflammation in respective subject primary skin fibroblasts.

#### **9. Off Study Criteria**

- Subjects taking less than 75% of the supplement
- Completion of study visits in pre-specified time windows
- Subjects who are found to be pregnant or wish to breastfeed during the study will automatically be withdrawn.
- Heart failure decompensation resulting in hospitalization.
- Any other severe medical symptoms that may or may not be related to the NR supplement and as determined by contact with the physician. *Note: IRB will be notified of any removal of research subject for severe medical symptoms, including heart failure decompensation.*

#### **10. Data and Safety Monitoring**

##### **Safety Monitoring**

**Principal Investigator:** Accrual and safety data will be monitored by the Principal Investigator at each site.

**NIH IRB:** Accrual and safety data will be monitored and reviewed annually by the Institutional Review Board (IRB). Prior to implementation of this study, the protocol and the proposed subject informed consent document will be reviewed and approved by the properly constituted IRB operating according to the 45 CFR 46. This committee must approve all amendments to the protocol or informed consent document, and conduct continuing annual review so long as the protocol is open to accrual or follow up of subjects. The NIH IRB will have full oversight of all activities conducted at WRNMMC as the IRB of Record. A reliance agreement between NIH and WRNMMC has been executed.

**DSMB:** The NHLBI Data Safety and Monitoring Board (DSMB) will review the protocol at six or twelve month intervals. A progress report will be forwarded to the DSMB at these times.

### **Adverse Event Reporting**

**Adverse Event (AE):** Any untoward medical occurrence in a human subject, including any abnormal sign (e.g., abnormal physical exam or laboratory finding), symptom, or disease, temporally associated with the subject's participation in the research, whether or not considered related to the subject's participation in the research.

**Serious Adverse Event (SAE):** A serious adverse event that:

- results in death;
- is life-threatening (places the subject at immediate risk of death from the event as it occurred);
- results in in-patient hospitalization or prolongation of existing hospitalization;
- results in a persistent or significant incapacity;
- results in a congenital anomaly/birth defect; or
- based upon appropriate medical judgment, may jeopardize the subject's health and may require medical or surgical intervention to prevent one of the other outcomes listed in this definition.

**Unanticipated Problem:** An UP is any incident, experience, or outcome that meets all of the following criteria:

1. **unexpected** in terms of nature, severity, or frequency in relation to
  - a. the research risks that are described in the IRB-approved research protocol and informed consent document; Investigator's Brochure or other study documents; and
  - b. the characteristics of the subject population being studied; and
2. **related or possibly related** to participation in the research; and
3. places subjects or others at a **greater risk of harm** (including physical, psychological, economic, or social harm) than was previously known or recognized.

### **Reporting of Pregnancy:**

In the event a subject becomes pregnant while on study, this event will be reported to the IRB and Clinical Director as an unanticipated problem. Monitoring of the pregnancy will continue until conclusion of the pregnancy.

***Unanticipated Problem that is not an Adverse Event:*** An unanticipated problem that does not fit the definition of an adverse event, but which may, in the opinion of the investigator, involves risk to the subject, affect others in the research study, or significantly impact the integrity of research data. For example, report occurrences of breaches of confidentiality, accidental destruction of study records, or unaccounted-for study drug.

***Protocol Deviation (PD):*** Any change, divergence, or departure from the IRB approved research protocol.

***Non Compliance:*** The failure to comply with applicable NIH HRPP policies, IRB requirements, or regulatory requirements for the protection of human research. Noncompliance may be further characterized as:

***Serious non-compliance:*** Non-compliance that:

- a. Increases risks, or causes harm, to participants.
- b. Decreases potential benefits to participants.
- c. Compromises the integrity of the NIH HRPP.
- d. Invalidates the study data.

***Continuing non-compliance:*** Non-compliance that is recurring. An example may be a pattern of non-compliance that suggests a likelihood that, absent an intervention, non-compliance will continue. Continuing noncompliance could also include a failure to respond to IRB requests to resolve previous allegations of non-compliance.

***Minor (non-serious) non-compliance:*** Non-compliance that, is neither serious nor continuing.

### **Adverse Event Management**

The principal investigators at WRNMMC or NIH, or designees, will be responsible for assessing adverse events. Information on adverse events will be solicited from subjects through questions from study personnel and information volunteered by the subject. Adverse events will be captured from the start of the first pill taken (day 0) until the completion of the washout phase of the study. The AEs will be attributed (unrelated, unlikely, possibly, probably or definitely) to study supplement and/or disease. This study will utilize the CTCAE version 5.0 for toxicity and adverse event reporting. A copy of the CTCAE version 5.0 can be downloaded from the [https://ctep.cancer.gov/protocolDevelopment/electronic\\_applications/ctc.htm](https://ctep.cancer.gov/protocolDevelopment/electronic_applications/ctc.htm). AEs will be recorded, verified, and followed until satisfactory resolution.

In the event of any treatment-related SAEs, enrollment will be suspended until discussed with the IRB and Clinical Director.

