### 3. Study Design and Procedures

The study design is an open label pilot study with subjects serving as their own controls. The outline of the clinical protocol is shown in a tabular schematic below.

Visit #	1	2	3	4	5	6	7A/B	8	9
Weeks	-1 to -3	0	0+ 1-2 days	2	4	6	12	12 + 1-2 days	16
Procedures									
History	X	X		X	X	X	X		X
Physical exam	X			X	X	X	X		X
Initiate NR/dispense meds			X						
Dose adjustment				X 	X 	X 			
Stop NR								X	
Urine pregnancy test	X 	X 	X 				X 	X 	X 
Clinical blood tests	(X)	X 	X 	X	X	X	X 	X 	X
NMR spectroscopy		X 	X 				X 	X 	X
CPET		X 	X 				X 	X 	
Echo	X*						X		
Research blood		X 	X 					X 	
Skin biopsy		X 	X 						
AE assessment				X	X	X	X	X	X
Concomitant meds/tx	X			X	X	X	X	X	X
Study drug adherence				X	X	X	X		
Key:									
(X) Performed only if baseline laboratory studies not performed during routine testing within 6 months									
X Procedure performed									
 Increase NR dose by 250mg BID									
 Pregnancy test will only be performed in women with childbearing potential. It can be completed at Visit 1, 2 and/or 3 and Visit 7 or 8									
 Skin biopsy will be completed at either Visit 2 or 3.									
 NMR spectroscopy, clinical and research blood, and CPET testing can be performed at either Visit 2 or 3 for baseline timepoint and Visit 7 or 8 for end of treatment timepoint.									
* Procedure is optional (Echo is optional on Visit 1 if PI feels there is an adequate and timely historical Echo)									
Visits 1, 4, 5, 6, and 7 may take place at either WRNMMC or NIH Clinical Center.									
Visits 2, 3, 7B, 8, and 9 will take place at the NIH Clinical Center									

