### **Grading and Attribution of Adverse Events**

**Severity.** Definitions found in the Common Terminology Criteria for Adverse Events version 5.0 (CTCAE v5.0) will be used for grading the **severity** (intensity) of AEs:

1 Mild	Asymptomatic or mild symptoms; clinical or diagnostic observations only; intervention not indicated.
2 Moderate	Moderate; minimal, local or noninvasive intervention indicated; limiting age-appropriate instrumental ADL*
3 Severe	Severe or medically significant but not immediately life-threatening; hospitalization or prolongation of hospitalization indicated; disabling; limiting self-care ADL**.
4 Life-threatening	Life-threatening consequences; urgent intervention indicated.
5 Death	Death related to AE

\*Instrumental ADL refer to preparing meals, shopping for groceries or clothes, using the telephone, managing money, etc.

\*\*Self-care ADL refer to bathing, dressing and undressing, feeding self, using the toilet, taking medications, and not bedridden.

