### *Attribution of Adverse Events*

Relationship	Attribution	Description
Unrelated to intervention	Unrelated	The AE is clearly NOT related to the intervention
	Unlikely	The AE is doubtfully related to the intervention
Related to intervention	Possibly	The AE may be related to the intervention
	Probably	The AE is likely related to the intervention
	Definitely	The AE is clearly related to the intervention

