#### ***The following adverse events will not be recorded or reported to the IRB.***

- Grade 1 adverse events
- Grade 2 laboratory abnormalities not associated with clinical signs or symptoms except for grade 2 elevated liver enzymes, which will be recorded and reported.

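### Adverse-event capture starts at the first pill, so a recordable, already-listed harm of the baseline exercise test or skin biopsy that begins before dosing may not be recorded as an adverse event

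*Combined protocol and SAP*

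**What the plan says.** All references are to the combined protocol and SAP.

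- **Definition.** Under Adverse Event Reporting, an adverse event is any untoward occurrence "temporally associated with the subject's participation in the research". Dosing is not part of the definition.
- **Capture window.** Under Adverse Event Management: "Adverse events will be captured from the start of the first pill taken (day 0"), and capture runs to the end of washout.
- **First pill.** The Visit 3 list starts the supplement that evening. Visit 3 falls one to two days after Visit 2.
- **Baseline procedures.** The schedule in section 3 allows CPET and spectroscopy at Visit 2 or 3. Its key also states: "Skin biopsy will be completed at either Visit 2 or 3". No other biopsy is planned.
- **Scheduled assessment.** The adverse-event row of the schedule is marked at Visits 4 to 9 and blank at Visits 1 to 3. The visit lists agree: Visit 4 is the first with an item for recording adverse events.
- **Recording threshold.** Under the heading "The following adverse events will not be recorded or reported to the IRB" the protocol lists Grade 1 events and "Grade 2 laboratory abnormalities not associated with clinical signs or symptoms except for grade 2 elevated liver enzymes, which will be recorded and reported".
- **Attribution.** "The AEs will be attributed (unrelated, unlikely, possibly, probably or definitely) to study supplement and/or disease". The attribution table rates relation to an intervention that it does not define.

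**The concern.** The capture window is narrower than the definition it is meant to serve. The three research procedures that every subject undergoes at baseline precede it. An event that meets the definition, is severe enough to be recorded and is caused by the research may have no place on the adverse-event form because it happened before the first pill. The same event at the Week 12 exercise test would be recorded.

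This does not look like a deliberate exclusion of procedure harms. The Waiver of Reporting section treats fainting symptoms and bruising from blood draws as adverse events and waives IRB reporting for those. Visit 8, where a CPET or a scan is done, does have adverse-event recording.

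What is at stake is the record of procedure safety. The Risk/Benefit Assessment calls the study greater than minimal risk with no prospect of direct benefit, and the research procedures are part of that risk. The IRB sees adverse events mainly through the summary at continuing review.

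**Working it through.** The plan gives no figure of its own on this point, so the check compares sections and then sizes the result.

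**Step 1. Is there a gap?** Capture opens at the first pill (Adverse Event Management). The first pill follows Visit 3 (Visit 3 list). Baseline CPET, spectroscopy and biopsy are at Visit 2 or 3 (schedule and visit lists). All three therefore precede the window. The mention of day 0 does not close the gap. Visit 2 is labelled Week 0, but the rule names the first pill, and neither Visit 2 nor Visit 3 has an adverse-event assessment on any reading.

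**Step 2. How long is it?**
- Procedure at Visit 3: from the procedure to that evening, which is hours.
- Procedure at Visit 2: to the evening of Visit 3, which is about one to two days.

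A harm that starts later, such as a biopsy infection after the first pill, is inside the window.

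**Step 3. Which events are affected?** Grade 1 events and most symptom-free Grade 2 laboratory abnormalities are not recorded at any time, so the loss is essentially Grade 2 and above.
- Biopsy: the Risks and Discomforts section lists anesthetic reaction, bleeding and infection. A bleed that needs local treatment fits the Grade 2 wording, "minimal, local or noninvasive intervention indicated".
- CPET: chest discomfort and rhythm disturbance are listed.
- Spectroscopy: the listed effects (nausea, metallic taste, light flashes, nerve stimulation that is at most mildly painful) read mostly as Grade 1, so little is lost here.

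**Step 4. Do other routes catch them?**
- An unanticipated problem must be unexpected in nature, severity or frequency, so a listed harm at its described level does not qualify. One that is worse or more frequent than described could.
- The removal note in section 9 reaches the IRB only if the subject is removed for severe symptoms.
- The Deaths rule covers related deaths only.

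What remains is a listed, non-fatal event of Grade 2 or above, with onset before dosing, that does not lead to removal.

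**Step 5. How many events?** Expected number = number of baseline procedures × rate per procedure, using the maximum enrolment of 25.
- Serious CPET complications: the stated rate is below 1 in 10,000 tests. 25 × 1/10,000 = 0.0025, so under 0.0025.
- MRI events: the MR Spectroscopy risk text reports one temporary eye complaint and one temporary hearing loss, each set against more than 5,000 subjects. 25 × 2/5,000 = 0.01, so about 0.01 or fewer. This assumes that the general scanner experience carries over to these scans. It counts events of any grade.
- Blood draws: the stated 50% for fainting symptoms and 50% for bruising do not add to the loss in IRB reports, because reporting of both is waived.
- Grade 2 or above after CPET or biopsy: the documents give no rate, so no expected number is offered.

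**The case against.** The strongest reply is that very little is left once the exclusions are applied: mostly a listed Grade 2 event within hours to about two days. The baseline CPET is run under EKG and blood-pressure monitoring by a nurse and a licensed practitioner, so such an event would be seen and managed. Only its entry as an adverse event is in doubt. Listed events that are not unanticipated problems get no expedited IRB report after dosing either, so the practical difference is mainly a line in the continuing-review summary. All of this stands, and it is why the severity is low.

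It can also be said that the continuing-review rule asks for all adverse events, and that the definition covers pre-dose events, so staff might include them. That is a fair reading. The text is unclear rather than clearly excluding, and the point is therefore that such an event could be left out, not that it must be. But with no assessment scheduled and a capture rule that starts later, inclusion would depend on individual initiative.

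Three stronger readings are tempting and are not supported:

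- **That half of the procedure harms are lost.** By the schedule and the compensation table, three of six such procedures per completing subject (one of two CPETs, one of three scans, the only biopsy) precede the window. That counts procedures, not events. One of the three is a scan with mostly Grade 1 harms, and later-onset harms are captured. A cohort total would also need assumptions about who leaves before Visit 2 and when others drop out.
- **That pre-dose harms have no reporting route at all.** Unanticipated problems, related deaths and removals for severe symptoms are covered.
- **That the attribution scale is defective because it has no procedure category.** Attribution is to supplement and/or disease, so a procedure-caused event can be read as "Unrelated to intervention". The unanticipated-problem test and the Deaths rule consider research procedures where that triggers a report. A procedure category would be useful but is optional.

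**Conclusion.** The concern holds in a limited form. The adverse-event definition and the capture rule disagree, and the schedule follows the narrower one. A listed, non-fatal harm of Grade 2 or above from a baseline procedure, chiefly the CPET or biopsy, that starts before the first pill is not captured under the stated rule unless it is an unanticipated problem or leads to removal for severe symptoms. It could be absent from the continuing-review summary.

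The size is small: hours to about two days per subject, and expected numbers well below one for the two kinds of event whose rates the documents give. Those figures rest on 25 baseline tests and scans and on the protocol's own rates. The number of Grade 2 or above CPET and biopsy events cannot be estimated from the documents.

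The primary comparison of phosphocreatine recovery time, its test and its sample size are unaffected. Severity is low; the case for acting is that the correction is cheap.

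**What to change.** 1. Reconcile Adverse Event Management with the definition in Adverse Event Reporting by starting capture at the first research procedure.
2. Mark an adverse-event assessment at Visits 2 and 3 in the section 3 schedule, and add the item to those visit lists.
3. Report pre-dose events separately from those on the supplement and in washout, so that the supplement's safety summary is not mixed with baseline procedure events.
4. Keep the existing recording threshold for Grade 1 events and symptom-free laboratory findings.
5. Optionally, add study procedure as an attribution target in Adverse Event Management and in the attribution table, in line with the Deaths paragraph, which already names procedures.

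The cost is a few sentences, two schedule boxes and slightly more case-report-form entry at visits that already take place.

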### **Visit 9 (Week 16 ± 1 week, NIH)**

The following procedures will be performed at the final study visit (Day 112 ± 5)

- Medical history, physical examination, current medical treatments
- Blood draws will analyze: CBC+Diff, proBNP, HbA1C, uric acid, ALT, CK, Chemistry panel (electrolytes, glucose, blood urea nitrogen and creatinine) and insulin levels.
- Pregnancy test on women with childbearing potential
- Record of adverse events, if any
- Record of concomitant medications or interventions, if any
- Skeletal muscle exercise NMR spectroscopy

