## **8. Statistical Considerations**

#### ***Primary study outcome:***

Continuous data will be presented as mean  $\pm$  standard deviation or median and range, as appropriate. The primary outcome of this pilot study will be the comparison of baseline to 12-week (on NR) skeletal muscle fixed-load sub-maximal exercise NMR spectroscopy skeletal muscle phosphocreatine recovery time. We are proposing a novel study with no data available on the effect of NR on mitochondrial function as measured in-vivo as measured by NMR spectroscopy. However, we appeal to data in Wang, et. al (ref. 20) to aid with a preliminary sample size calculation. In the Wang, et. al. study, the mean recovery time in leg muscle

phosphocreatine levels after foot-exercise in the control group was  $36.7 \pm 6.6$  seconds. Based on the paired t-test, a sample of size 15 will allow our study to detect a 13% or greater relative reduction (4.8 sec or greater absolute reduction from 36.7 sec to 31.9 sec) in skeletal muscle recovery time with NR at 12 weeks compared to baseline with 80% power and a two-sided alpha of 0.05. The calculation assumes that the standard deviation of the recovery times of the paired baseline to 12-week differences on NR is the same as the standard deviation of the phosphocreatine recovery times in the control group (i.e. 6.6 sec) of the Wang, et. al. study. We request the enrollment of 20 subjects to allow for subject attrition and a margin of error for the study assumptions. The primary analysis of the primary endpoint will use a non-parametric Wilcoxon Signed Rank test for paired data.

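### Adverse events are to be captured to the end of washout, but no contact is planned for subjects taken off study early, so new events after removal may be missed

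*Combined protocol and SAP*

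**What the plan says.** - **AE window.** Section 10, Adverse Event Management, has AEs captured from the first pill on day 0 "until the completion of the washout phase of the study". No exception is made for subjects who leave early. The same section adds: "AEs will be recorded, verified, and followed until satisfactory resolution". Staff are to ask about events and also to accept what subjects report unprompted.
- **Removal.** Section 9 is headed as off-study criteria, not off-treatment criteria. The list includes "Heart failure decompensation resulting in hospitalization", "Subjects taking less than 75% of the supplement", other severe symptoms whether or not related to NR, and pregnancy or a wish to breastfeed. It also includes ordinary completion of the visits. A note says the IRB is told of removals for severe symptoms, HF decompensation included.
- **Visits.** In the Section 3 schedule, AE assessment is marked at Visits 4 to 9 only. Visit 9, at week 16, is the last, and its list includes "Record of adverse events, if any". No early-termination visit, safety call or record check is described.
- **Pregnancy.** Section 10 (Reporting of Pregnancy) continues monitoring until the pregnancy ends. This is the only withdrawal reason with its own rule for what happens afterwards.
- **Numbers.** Sections 2 and 3 allow up to 25 subjects in order to have 15 completers. Section 8 says: "We request the enrollment of 20 subjects to allow for subject attrition", and the same sentence adds a margin for the study assumptions.

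**The concern.** The AE window is defined for everyone, but the means of observing it are defined only for subjects who keep to the visit schedule. Someone removed at week 4 has no later study contact on paper, although the window in Section 10 still has weeks to run. Section 10 also defines an AE by its timing relative to participation in the research. If removal ends participation, a later event might not be treated as an AE at all.

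Two of the removal reasons, HF hospitalization and other severe symptoms, are themselves possible harms. Follow-up that shortens for those reasons is not missing at random with respect to safety.

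The study is open label with no control arm, so its own safety evidence is what is recorded in dosed subjects. Section 11 notes the absence of reported human experience with repeated dosing at the final level. Section 10 suspends enrollment on any treatment-related SAE until it has been discussed with the IRB and Clinical Director. An SAE that begins after removal and is never learned of cannot reach that trigger.

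**Working it through.** The plan gives no figure on this point to reproduce. The check has two steps: a comparison of the text, then the size of the possible gap.

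**Step 1. What the plan would observe in a subject removed before week 16**

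| Event | Captured as written? | Basis |
|---|---|---|
| HF hospitalization that triggers removal | Yes | Meets the SAE definition in Section 10; IRB told under Section 9 |
| Later course of that same event | Yes, to resolution | Adverse Event Management |
| Pregnancy | Yes, to its end | Reporting of Pregnancy |
| Related death of which the PI learns | Reported within 7 days | Deaths; no planned means of learning of it |
| New AE or SAE starting after removal | Only if volunteered or met by chance | No visit, call or record check scheduled |

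The gap is the last row, together with deaths that nobody reports to the PI.

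**Step 2. Size, if capture stops at removal.** This is an assumption; the documents do not say so.

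Inputs: up to 25 enrolled and 15 to complete (Sections 2 and 3), and 16 weeks from start to final visit (Section 3). Removal is assumed at week 2, 6 or 12, which are visit weeks in the schedule.

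- Planned person-weeks: 25 x 16 = 400.
- Weeks lost per removed subject: 16 - 2 = 14; 16 - 6 = 10; 16 - 12 = 4.
- Share unobserved = k x (16 - week of removal) / 400, where k is the number removed.

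| Removed (k) | At week 2 | At week 6 | At week 12 |
|---|---|---|---|
| 1 of 25 | 14/400 = 3.5% | 10/400 = 2.5% | 4/400 = 1.0% |
| 5 of 25 | 70/400 = 17.5% | 50/400 = 12.5% | 20/400 = 5.0% |
| 10 of 25 | 140/400 = 35% | 100/400 = 25% | 40/400 = 10% |

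Ten is the whole allowance, 25 - 15. With the 20 subjects of Section 8 there are 20 x 16 = 320 planned person-weeks, and 5 removed would leave 20/320 = 6.3% to 70/320 = 21.9% unobserved.

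**A second reading of the window.** The end of washout is fixed only by the completers' schedule. For a subject who stops early it could mean week 16, as above, or 4 weeks after the last dose. On the latter reading, and if the last dose is taken at removal, each removed subject loses 4 weeks whenever removal occurs: 5 x 4 = 20 person-weeks for five subjects and 10 x 4 = 40 for ten. The plan should say which reading applies.

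**The case against.** The strongest reply is that no conflict is stated. Only Section 10 gives an AE end point, and it makes no exception. Section 9 never says that AE capture stops. Its list includes subjects who simply complete, and pregnant subjects are withdrawn yet still monitored, so off-study status does not by itself end safety follow-up. Volunteered reports are accepted, and a subject removed for an HF hospitalization stays under follow-up until that event resolves, when a readmission might well come to light.

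Most of this stands, and it rules out several stronger readings:

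- **A reader might infer that the plan sets two different AE end points.** It sets one. What is missing is a means of observing removed subjects up to it.
- **A reader might infer that harmed subjects drop out of the safety count.** They do not. The triggering hospitalization is an SAE, is followed, is notified to the IRB and is summarised at continuing review. A count of subjects with at least one SAE already includes that subject. Only new events are at risk.
- **A reader might infer that all removed subjects are at higher risk.** Low intake alone does not show that.
- **A reader might infer a known downward bias in an AE rate.** Section 8 defines no AE rate or other safety endpoint, and the documents give no event risks for removed or completing subjects. Any figure for the share of events captured would rest on invented risks, so none is given here.

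What does not stand is the view that volunteered reports are enough. They are not systematic, and nothing in the schedule prompts them after removal.

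**Conclusion.** The point holds in limited form. As written, the plan does not provide the means to deliver its own AE window for subjects taken off study early. For removals due to HF hospitalization or severe symptoms, the part that may be lost is related to possible harm.

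The range of 5.0-17.5% of planned person-weeks for 5 of 25 removed, and 10-35% for 10 of 25, is a bound on unobserved time, not an estimate of missed events. It assumes that all 25 are dosed, that capture stops completely at removal, that removal falls between weeks 2 and 12, and that the window runs to week 16 for everyone. The counts of 5 and 10 are also illustrative. The margin in Section 8 is not purely for attrition, some non-completers may leave for reasons outside Section 9, and some of those enrolled may never be dosed. With a single removal the gap is 1.0-3.5%.

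**What to change.** Reconcile Sections 9 and 10 as follows.

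- State that off-study status does not end capture of AEs, SAEs and deaths.
- State the post-NR window explicitly, the same as for completers, and say how it is counted for a subject who stops early.
- Follow every dosed subject to the end of that window, by telephone contact or medical-record check where no visit is made.
- Report AEs for all dosed subjects over that window.

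What each Section 9 criterion means for supplement use is for the sponsor to settle; this point does not depend on it.

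The cost is a sentence in each section and about one call or chart check per removed subject, so roughly 5 to 10 contacts if 5 to 10 subjects are removed. The downside is a possibly less favourable AE count.
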